7.2.1 Secondary Objective Analyses (if applicable)

Phase 1: Not applicable

Phase 2: See above analysis plan for primary and secondary outcomes.

7.2.2 Analysis of Subject Characteristics (if applicable)

Phase 1: Not applicable

Phase 2: Descriptive analyses will be performed to describe demographic and clinical characteristics of the sample.

7.2.3 Interim Analysis (if applicable)

Phase 1: Not applicable

Phase 2: Not applicable

7.3 Data Relevance

Phase 1: Qualitative data collected from our stakeholders – healthcare providers/community health workers of CHCs and adults with T2D who access care at CHCs – will provide information on the barriers, facilitators, and needs related to an intervention to increase patient portal use for diabetes care. This will allow us to complete our study aim which is to optimize components of the *MAP* intervention for adults with T2D who access healthcare at CHCs. We will use these qualitative findings to finalize the *MAP* protocol.

Phase 2: Data collected from participants, the electronic medical record, and patient portal will provide important information on whether the provision of material resources (tablet and data plan), technology assistance, and nursing education and support increases use of the patient portal and engagement with diabetes care. Adults with T2D who access clinical care at community health centers often do not have consistent engagement with clinical care, particularly through the patient portals. Use of patient portals has been shown to improve health care outcomes; thus, the data in this study will help us understand if our approach has the potential to improve health outcomes in this population.

7.4 Data Coding

Phase 1: We will use established content analysis procedures to code the data. Initially we will develop coding categories by two members of the research team. Next we will assign codes to text in our transcripts with appropriate checks (having the 2 coders independently

code the first 2 transcripts and check codes for agreement and resolve discrepancies). If the 2 coders cannot resolve discrepancies, these will be discussed with the Co-PIs. Once all data are coded, we will review coded data to identify themes across participants. During this process, we will use a team approach to data analysis to enhance rigor. At research team meetings we will assess researcher bias, coding saturation, and interpretative congruence.

Phase 2: Quantitative data will be coded based on a pre-determined system (either by assigning a number to specific characteristic or by following questionnaire scoring guidelines). De-identified data from REDCap will be downloaded into our statistical software for data analysis. For open-ended questions on Technology Barriers and Facilitators, we will use a content analysis method to code participant responses into categories in order to describe the most common barriers and facilitators.

7.5 Data Analysis Tools

Phase 1: We will use SAS or EXCEL to describe the sample. We will use NIVIVO, a qualitative data analysis software to analyze interview data.

Phase 2: We will use SAS or EXCEL to describe the sample.

7.6 Data Monitoring

Phase 1: Not applicable

Phase 2: The co-PIs ([name] and [name]) are responsible for monitoring individual events and determining whether the study protocol needs modification to minimize risk.

The research team will have at least monthly meetings to review individual cases and ensure close monitoring of participants. If the team considers it appropriate, with a signed release of information from the participant, we will give any relevant information regarding the participant's health to their medical care providers.

7.7 Handling of Missing Data

Phase 1: Not applicable

Phase 2: To confirm findings with missing data, we will rerun the GLMM with multiple imputations which will be produced by assuming multivariate normal distribution of repeatedly measured A1C. Number of logins and the repeatedly measured secondary outcomes will be analyzed with the same approach using the GLMM.

8 Data/Specimen Handling and Record Keeping

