Glycosylated Hemoglobin (A1C)	A1C now point of care with fingerstick of blood
Secondary:	
Engagement with care	Clinic appointments Referrals ER visits Hospitalizations Use of community resources
T2D clinical management	EMR data: dates of service, A1C, blood pressure, lipid profile, height, weight, BMI
T2D self-management	Self-rated health (1 item); Medication adherence, blood glucose monitoring, healthy eating, physical activity (24 items)
Psychosocial outcomes	Diabetes self-efficacy (8 items) Autonomy support (health care climate) (7 items) Diabetes distress (20 items)
Technology acceptance/use	Digital health literacy (3 items) Technology acceptance (8 items) Technology use (6 items) Technology confidence (4 items) Tablet use (3 items)

	Barriers/Facilitators (13 items)
Satisfaction	Satisfaction with program (4 items) Satisfaction with health care provider (3 items)
Use of community resources	1 items

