6.5 Withdrawal Procedures

Phase 1: Not applicable

Phase 2: Participants will be informed that their participation in the study is voluntary and they are free to withdraw at any time and withdrawal from the study will not affect their relationships with anyone at the clinic. Participants who withdraw from the study will keep the tablet provided from the study.

Withdrawal of enrolled participants who develop any of the exclusionary or potentially exclusionary criteria (e.g., pregnancy) will be assessed on a case by case basis depending on the severity and whether there are any potential risks to following the study protocol. The decision to withdraw a participant from the study will be ultimately made by the co-PIs. Data and/or sample collection will be discontinued depending on the severity of the condition. Should a participant develop an exclusionary condition, he or she will be given the opportunity to continue. He or she will also be given the opportunity to opt out from data collection even when the co-PIs had considered appropriate to continue collecting data.

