7.2 Planned Analyses

Phase 1 analysis:

The sample of participants in the interviews/focus groups will be described using frequency distributions and appropriate summary statistics (SAS version 9.4). Content analysis will be used to analyze qualitative data from each type of stakeholder along with field notes and interviewer observations (Hsieh, 2005) Rigor for this process includes: (a) transcribing taped interviews; (b) checking transcripts against tapes for accuracy; (c) developing coding categories by two members of the research team; (d) assigning codes of text with appropriate checks; (e) reviewing coded data to identify themes across participants; and (f) a team approach to data analysis. At research team meetings we will assess researcher bias, coding saturation, and interpretative congruence. Results will be used to finalize the intervention protocol for implementation in Phase 2

Phase 2 Analysis: Data will be collected in the form of questionnaires online on the secure REDCap system. A1C data, electronic medical record data and patient portal data will be entered into REDCap or Excel and merged into one database. All data that are downloaded from REDCap or Excel will be onto a Yale server, which has several secure firewall systems. Descriptive analyses will be performed to assess demographic and clinical characteristics of the sample. Feasibility data will be summarized. Distributions of outcome variables will be examined for central tendency and dispersion. We will estimate the Cohen's D effect size of MAP on A1C and will examine the intervention effect over 6 months using generalized linear mixed model (GLMM) with random intercept, which will incorporate the correlation within repeatedly measured A1C. The slope of time will represent the average change of A1C over 6 months. The GLMM will include all participants with data at baseline and at least one of post-intervention value and will handle missing data using maximum likelihood approach. To confirm findings with missing data, we will rerun the GLMM with multiple imputations which will be produced by assuming multivariate normal distribution of repeatedly measured A1C. Number of logins and the repeatedly measured secondary outcomes will be analyzed with the same approach using the GLMM. Residuals will be assessed for normality assumption and

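### The one stated check on missing A1C data shares the main model's missing-at-random assumption, so agreement between the two says little about whether people lost from assessment did worse

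*Combined protocol and SAP*

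**What the plan says.** Section 7.2 estimates the A1C change over 6 months "using generalized linear mixed model (GLMM) with random intercept, which will incorporate the correlation within repeatedly measured A1C". The model "will handle missing data using maximum likelihood approach". Its analysis set is restricted: "The GLMM will include all participants with data at baseline and at least one of post-intervention value". A participant with a baseline value only is therefore left out.

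Sections 7.2 and 7.7 then give one check: "To confirm findings with missing data, we will rerun the GLMM with multiple imputations which will be produced by assuming multivariate normal distribution" of the repeatedly measured A1C. Section 7.7 extends the approach: "Number of logins and the repeatedly measured secondary outcomes will be analyzed with the same approach using the GLMM".

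Neither section names the missing-data assumption. Neither plans a shifted imputation, a tipping-point analysis, auxiliary variables in the imputation, or a comparison of leavers with stayers.

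Section 6.5 tells participants that "they are free to withdraw at any time", and section 7.1 allows for no dropout. Table 1 in section 6.1.1 lists, as a secondary measure, "EMR data: dates of service, A1C, blood pressure, lipid profile, height, weight, BMI". The plan does not say that this record is used to fill or test missing study fingerstick values.

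**The concern.** A sensitivity analysis tests an assumption only if it relaxes that assumption. Here the main model and its check use the same observed A1C values and both require missingness to depend only on what was observed. If people lost from assessment do worse than their observed values predict, both analyses miss it by about the same amount, and their agreement would be read as reassurance.

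The stakes come from the design. There is no control arm, so bias from loss to assessment falls directly on the estimated change. The primary objective of Phase 2 (section 3.3) is an effect size, and section 7.1 presents the pilot as groundwork for a larger study. An A1C change that is too favourable would carry over into that study's planning.

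**Working it through.** **Step 1. What each analysis assumes.** Maximum likelihood on a normal mixed model is valid when the chance of a value being missing depends only on observed values. Multivariate normal imputation draws each missing value given the person's observed values, with parameters estimated from the same data, and needs the same condition. Neither has a parameter that lets unseen values differ systematically from their prediction. The two differ only in covariance form, in the shape of time, and in imputation noise.

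**Step 2. The plan's precision figure, for scale.** From section 7.1: SE = 0.72/√30 = 0.131; margin = 2.045 × 0.131 = 0.269, which agrees with the stated ±0.27. The 0.72 does not itself follow from the stated SD of 1.2 and correlation of 0.57: 1.2 × √(2 × (1 − 0.57)) = 1.113, giving SE 0.203 and ±0.416. That is a separate matter; both margins serve here only as a scale.

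**Step 3. Size by arithmetic.** If a proportion p is lost and their unseen A1C is higher by δ than missing at random predicts, the true mean change is the modelled change plus pδ. The bias is therefore about −pδ (the fall in A1C is overstated).

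**Step 4. Simulation over a range.** From the documents: n = 30, three visits, SD 1.2, correlation 0.57. Assumed: a change of −0.5 before any shift; 3, 6 or 9 people lost, half (rounded down) before month 3 and the rest between months 3 and 6; δ = 0, 0.5 or 1.0. There were 600 trials per setting, 20 imputations each, and a Monte Carlo SE of about 0.009. Bias in % A1C:

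| Lost | δ | −pδ | ML | Planned MI | MI shifted by δ |
|---|---|---|---|---|---|
| 3/30 | 0.5 | −0.05 | −0.05 | −0.05 | 0.00 |
| 3/30 | 1.0 | −0.10 | −0.10 | −0.10 | 0.00 |
| 6/30 | 0.5 | −0.10 | −0.10 | −0.10 | 0.00 |
| 6/30 | 1.0 | −0.20 | −0.20 | −0.20 | 0.00 |
| 9/30 | 0.5 | −0.15 | −0.13 | −0.14 | +0.02 |
| 9/30 | 1.0 | −0.30 | −0.30 | −0.30 | 0.00 |

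With δ = 0 all three are unbiased within simulation error. The shifted imputation recovers the truth because it is given the true δ; the point is that it can move, and the planned one does not. ML and planned MI estimates correlate 0.96 to 0.99, and the SD of their difference is 0.03 to 0.06, whether or not leavers do worse. With 6 lost and δ = 1.0, coverage of the 95% interval is 85% for ML, 88% for planned MI and 96% for the shifted version. Imputing the baseline-only people under the planned model, or leaving them out, changes the mean by 0.002 or less.

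**Step 5. Leavers who do not change.** Assume 24 stay and improve by 0.5, and 6 leave with no change (3 after baseline, 3 after month 3). The expected mean change is 24 × (−0.5)/30 = −0.40. In 400 simulated trials the full-data mean was −0.420, ML gave −0.508 and the multivariate normal model gave −0.508. The bias is −0.508 − (−0.420) = −0.088, or 0.088/0.420 = 21%. The two estimates correlated 0.996 and differed by 0.016 on average. It falls slightly short of 0.2 × 0.5 = 0.10 because three leavers contribute an unchanged month-3 value. Setting leavers' missing visits to no change, with all 30 included, gave −0.412; that matches the simulated truth by construction.

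**The case against.** Missing at random is a standard primary assumption, and this is an uncontrolled pilot of 30 with no specified hypotheses (section 3.2). Both statements are fair, and the point leaves the primary model alone. But the effect size is what the pilot is meant to deliver.

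The imputation is not an empty rerun. It is not tied to a random intercept and a linear slope, so it can show sensitivity to model form. That is a reason to keep it.

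The plan also yields a second A1C series. EMR A1C is a secondary outcome (section 4.2.2), extracted by clinic staff (sections 6.6 and 8.5) and analysed with the same approach. This is a partial answer: it is not designated as a missing-data check and does not enter the imputation.

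The size is modest in milder settings. A bias of 0.09 is about 0.4 of the estimate's sampling SD (0.22 in simulation).

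A reader might infer more than the documents support:
- *The check will always confirm the main result.* This is only a tendency. In simulation the two significance verdicts agreed in 88 to 97% of trials; the rest reflect noise and covariance form, not detection of bias.
- *Anyone who stops MAP is imputed as still improving.* Someone who stops but attends assessments is observed. Section 6.1 plans reminders, escalating payments and alternate contacts, and section 6.6 allows A1C to be taken away from the clinic. A poor month-3 value also enters both analyses.
- *Logins are lost in the same way.* Clinic staff export portal data (sections 6.6 and 8.5), so loss at withdrawal is not shown.

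**Conclusion.** The point stands in a limited form. The only stated missing-data check for the primary A1C result shares the main model's missing-at-random assumption, so agreement between them is weak evidence about people lost from assessment. The assumption is not named in the documents; it follows from the methods.

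The bias is about the dropout proportion times the leavers' A1C difference: about 0.09% A1C in the 6-of-30 no-change scenario, and 0.05 to 0.30 across 10 to 30% dropout with leavers 0.5 to 1.0% worse. Against the stated ±0.27 margin, 0.09 is a third and 0.30 slightly exceeds it; against ±0.416 they are about 22% and 72%. Dropout, leaver behaviour and the −0.5 improvement are all assumptions.

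The documents do not show that the estimate will be biased. If leavers do no worse than predicted, there is no bias. The difficulty is that the planned check looks much the same either way. The remedy is a cheap improvement to the plan; the primary analysis need not change.

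**What to change.** In sections 7.2 and 7.7, keep the planned imputation but describe it as a check on model form under missing at random, and not as confirmation against missing data. Add a pre-specified sensitivity analysis covering all 30 enrolled. State that the rule requiring a post-baseline value does not apply to it, so that baseline-only participants are included. Run two separate scenarios:

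- (a) Impute missing post-baseline A1C around the person's own baseline, with no mean change and with random variation.
- (b) Shift the missing-at-random imputations upward over a stated range, for example +0.25 to +1.0% A1C. The documents give no basis for a particular range, so it is the sponsor's choice.

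For each, report how far the 6-month change and its confidence interval move from the main result.

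Where the participant still permits use of the record, include the dated EMR A1C as an auxiliary variable in the imputation, not as a substitute for the fingerstick value. Section 6.5 does not say whether the record may be used after withdrawal, so the plan should.

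For logins, use the exported counts. A zero-login scenario is not needed unless exports are actually missing.

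Cost: SAP wording and a few extra runs on data already collected. The downside is that the sensitivity results may look less favourable than the main one.

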8.1 Subject Data Confidentiality

Phase 1 and Phase 2: Participant confidentiality and privacy is strictly held in confidence by the participating investigators, their staff, and the sponsor(s)/funding agency. Therefore, the study protocol, documentation, data, and all other information generated will be held in strict confidence. Participants of focus groups will be informed not to divulge information they would not want repeated outside the focus group.

All research activities will be conducted in as private a setting as possible.

Representatives of the Institutional Review Board (IRB), regulatory agencies or study sponsor/funding agency may inspect all documents and records required to be maintained by the investigator for the participants in this study. The study site will permit access to such records.

The study participant's contact information will be securely stored at each study site for internal use during the study. At the end of the study, all records will continue to be kept in a secure location for as long a period as dictated by the reviewing IRB, Institutional policies, regulatory, or sponsor/funding agency requirements.

Study participant research data, which is for purposes of statistical analysis and scientific reporting, will be transmitted to and stored on the Yale Server that is password protected with multiple firewalls. This will not include the participant's contact or identifying information. Rather, individual participants and their research data will be identified by a unique study identification number. The study data entry and study management systems used will be secured and password protected. At the end of the study, all study databases will be de-identified and archived in a secured file on the Yale server.

8.2 Data Quality Assurance

Phase 1: The Co-PIs have experience with conducting formative research to inform intervention development. We also have expertise in the collection and analysis of qualitative data. The Co-PIs will train all research team members who will be obtaining informed consent, collecting data, and coding data for this phase of the study. We will provide research assistants with the opportunity to practice obtaining informed consent and collecting data with semi-structured interviews. We will review the transcripts of the first 3 interviews for training purposes. We will also develop and maintain a study manual which will provide resources and documentation of all study procedures.

Phase 2: The Co-PIs have expertise in the conduct of intervention development and evaluation research, implementing interventions, monitoring the fidelity of the intervention delivery, and collecting data accurately and consistently .The Co-PIs will train all research

team members who will be obtaining informed consent and collecting data. We will provide research assistants with the opportunity to practice obtaining informed consent and will debrief at research meetings. We will also develop a manual of study operation procedures and forms that will be available to all study personnel.

We will create a manual for the study interventionists on assisting participants with technology and on the nursing education and support component of the intervention. All interventionists will be trained by the Co-PIs and will be asked to demonstrate competency in role-play situations prior to engaging with study participants. Study interventionists will meet with the co-PIs weekly for the first 4 weeks and bi-weekly thereafter to review how things are going with study implementation and to discuss successes and challenges. The PIs will also be available to study interventionists for any questions that arise in between meetings. Intervention fidelity will be assessed by study interventionists and will be reviewed by the PIs. Any difficulties with protocol implementation will be addressed with the interventionists.

8.3 Data or Specimen Storage/Security

Phase 1: Data will be stored in a secure, password protected file on the Yale server.

Phase 2: Data will be stored in a secure, password protected file on the Yale server.

8.4 Study Records

Phase 1: Study records include regulatory documents, the protocol, consent forms, subject demographic information, and interview data. The Yale PI will be responsible for maintaining the study documentation. Files that need to be shared by research team members will be in a Secure Box folder on the Yale Server. Research team members include the Co-PIs, the study coordinator, and research assistants.

Phase 2: Study records include regulatory documents, the protocol, consent forms, subject demographic information, and participant data (study questionnaires, electronic medical data, patient portal data). The Yale PI will be responsible for maintaining the study documentation. Files that need to be shared by research team members will be in a Secure Box folder on the Yale Server. Research team members include the Co-PIs, the study coordinator, and research assistants.

8.5 Access to Source

Phase 1: Not applicable.

Phase 2: Source data consists of data collected from the electronic medical record and from the patient portal. Select personnel at each clinic will collect this data, record or export data to a study record form, de-identify the data, and securely transfer it to the PIs.

8.6 Retention of Records

Phase 1: Audio files will be destroyed as soon as the transcript has been checked. Transcripts of interviews (de-identified) will be maintained for one year or upon completion of a published manuscript of the aggregate data.

Phase 2: All data will be de-identified using a code number for each participant. De-identified data will be kept until all study results have been analyzed and manuscripts published or as long as legally required, whichever is longer and then destroyed.

